Day	Day -28 to -2	Day -1	Day 1	Day 15	Day 29	Day 57	Day 71	Day 85	Day 99	Day 113	Day 127	Day 141	Day 169	Day 197	Day 225							
Hour			Pre-dose 0 6	Pre-dose 0 6	Pre-dose 0 6	Pre-dose 0 6		Pre-dose 0 6	Pre-dose 0 6	Pre-dose 0 6		Pre-dose 0 6										
ESSDAI	X	X		X ⁶	X ⁶	X ⁶		X ⁶	X ⁶	X ⁶		X ⁶	X	X	X							
ESSPRI, MFI, SF-36		X				X ⁶		X ⁶		X ⁶		X ⁶	X	X	X							
VAS Assessments by Investigator and Patient		X		X ⁶	X ⁶	X ⁶		X ⁶	X ⁶	X ⁶		X ⁶	X	X	X							
Ultrasound		X ⁶						X ⁶							X							
Corporate Confidential Information		X						X ⁶					X		X							
	X							X ⁶					X		X							
		X						X					X		X							
		X ⁶						X							X							
		X													X							
		X													X							
PK blood collection			X	X	X	X	X	X	X	X	X	X	X	X	X							
Corporate Confidential Information		X											X	X	X							
Leukocyte subsets		X			X	X		X					X									
Corporate Confidential Information	X				X			X					X		X							
		X		X		X		X				X			X							
	X	X		X	X	X		X	X	X		X	X	X	X							
		X	X	X	X	X	X	X	X	X	X	X	X	X	X							
		X	X	X	X	X	X	X	X	X	X	X	X	X	X							
		X		X			X			X			X	X								
Study completion information															X							

¹ Placebo-Controlled Period includes Day 1 (Week 1) to completion of pre-dose assessments on Day 85 (Week 13). Open-Label Period includes Day 85 (dosing, Week 13) to completion of assessments on Day 169 (Week 25). Follow-Up Period includes Week 25 - Week 32.

² Visit 8 is the end of placebo-controlled period and the start of open-label period, Visit 13 is the end of open-label period and the start of follow-up period

³ The post-dose 6 h assessments should include assessing injection site(s) and vitals before dismissing the subject from clinical site

⁴ These should use serum pregnancy test

⁵ Serious Adverse Events reporting is required from signing the informed consent until 30 days after study completion

⁶ These pre-dose assessments can be done one day before the dosing or within 6 hours post dosing

Corporate Confidential Information

This assessment can be performed at screening

Corporate Confidential Information

* Patients who discontinue the study should complete these assessments

¹ Placebo-Controlled Period includes Day 1 (Week 1) to completion of pre-dose assessments on Day 85 (Week 13). Open-Label Period includes Day 85 (dosing, Week 13) to completion of assessments on Day 169 (Week 25). Follow-Up Period includes Week 25 - Week 32.

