² Visit 8 is the end of placebo-controlled period and the start of open-label period. Visit 13 is the end of open-label period and the start of follow-up period

³ Patients who discontinue the study should complete these assessments

⁴ This is 2 hours after the end of i.v. infusion

⁵ The post-dose 2 h assessments should include assessing infusion site and vitals before dismissing the subject from clinical site

⁶ These should use serum pregnancy test

⁷ Serious Adverse Events reporting is required from signing the informed consent until 30 days after study completion

⁸ These pre-dose assessments can be done one day before the dosing

⁹ This assessment can be performed at screening

¹⁰ PK samples should be taken from the other arm which has not been used for i.v. infusion
Corporate Confidential Information

* Baseline safety evaluation results must be available prior to dosing and meeting eligibility criteria

¹ Visit windows are specified in [Section 6](#)

² Pre-dose

³ Post dose assessments should include assessing injection sites, body temperature and vitals before dismissing the subject from clinical site.

⁴ Unstimulated salivary flow can be assessed at screening or baseline
Corporate Confidential Information

⁶ In treatment arm 1, subjects will receive CFZ533 s.c. at Visits 3, 4, 5, 6, and then s.c. at Visits 7, 8, 9, 10, 11, 12, 13, 14 and 15.

In treatment arm 2, subjects will receive CFZ533 i.v. at Visit 3, and then s.c. at Visits 4, 5, 6, 7, 8, 9, 10, 11, 12, 13, 14 and 15

⁷ This post-dose PK sample is for treatment arm 2 first dose (i.v.) only. The sample is taken at 1 hour after the end of the i.v. infusion. No post-dose PK sample is collected after s.c. injections at Visit 3 in treatment arm 1.

⁸ Patients who discontinue the study should complete these assessments

1 Introduction

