The end of study visit will occur on Day 225 (Week 33), which will include study completion evaluations followed by discharge from the study.

Cohort 2

Approximately 12 subjects would have been enrolled in Cohort 1, Cohort 2 will begin enrollment to randomize approximately 30 patients to have approximately 24 patients completing 12 weeks treatment. The study design for Cohort 2 is identical as Cohort 1 with the exception of the dosing regimen to include multiple intravenous dosing of CFZ533 followed by PK, pharmacodynamics (PD) and safety assessments for up to 2 hours after the end of the infusion. Additionally, body weight will be measured at every dosing visit to calculate the drug dosage according to the subject's actual weight (in Cohort 1, subject's baseline weight was used throughout study).

Cohort 3

All new patients enrolled after Protocol Amendment 6 will be allocated to Cohort 3. Cohort 3 will randomize approximately 24 patients to have approximately 20 patients (10 in treatment arm 1, 10 in treatment arm 2) completing a 12-week treatment.

Patients can remain on their standard of care therapies provided that the treatments are maintained at a constant level during the study.

Safety assessments will include physical examinations, ECGs, vital signs, standard clinical laboratory evaluations (hematology, blood chemistry, urinalysis, pregnancy test, blood coagulation), adverse event and serious adverse event monitoring.

All s.c. injections and i.v. infusions will take place in a monitored facility. Patients will be monitored closely for at least 6 hour after s.c. injection in Cohort 1, 2 hours after completion of i.v. infusion in Cohort 2. In Cohort 3, the patients will be monitored for at least 1 hour after the completion of i.v. infusion and 30 minutes after s.c. injection, or longer at the discretion of the Investigator for vital signs, and signs or symptoms of adverse events including development of an injection reaction. Treatment of injection site reaction and allergic reactions is described under [Section 5.5.6](#). Pharmacokinetic, pharmacodynamic, and safety assessments will be made for up to 6 hours after s.c. injection in Cohort 1, 2 hours after the completion of i.v. infusion in Cohort 2, or 1 hour after the completion of the i.v. infusion and 30 minutes after the s.c. injection in Cohort 3. Subjects will be discharged after these assessments, at the discretion of the Investigator, following satisfactory review of safety data.

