Subjects who discontinue study treatment should NOT be considered withdrawn from the study UNLESS they withdraw their consent (see [Section 5.5.11](#)). They should return for the assessments indicated by an asterisk (*) in the assessment table. If they fail to return for these assessments for unknown reasons, every effort should be made to contact them as specified in [Section 5.5.12](#).

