9.4.3 Handling of missing values/censoring/discontinuations

All subjects with a baseline ESSDAI and at least one post-baseline ESSDAI will be included in the primary analysis. The planned mixed effects model assumes that missing values are missing at random. The guidelines for subject discontinuation given in Section 5.5.10 should ensure that the missingness mechanism is as close as possible to missing at random.

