## **7 Statistical methods for Pharmacodynamic (PD) parameters**

### **7.1 Analysis of the primary variable**

#### **7.1.1 Statistical model, hypothesis, and method of analysis**

The primary efficacy variable is the ESSDAI change from baseline.

It is assumed that the ESSDAI will follow an approximate normal distribution. If this assumption appears to not be met, alternative statistical methods may be applied. For example, data may be log transformed with changes from baseline in the log transformed data being analyzed.

The analysis of the data for the primary variable from Cohorts 1 and 2 differs from that proposed in the protocol in that it will not be conducted combining placebo data from those two cohorts. Being in two separate consecutive cohorts, one s.c. and the other i.v., they are not now considered similar enough to combine. As a result, the active treatments under consideration, Corporate Confidential Information are each compared to their respective matching placebo treatments within each cohort. Cohort 3 simply compares two alternative loading regimes.

For each of cohorts 1 and 2, a longitudinal model describing ESSDAI change from baseline over time will be fitted up to Week 13 with the following fixed effect terms: baseline ESSDAI, treatment group, visit, and interaction between treatment group and visit. In the first instance an unstructured variance-covariance matrix will be fitted; if there are issues with convergence then other variance-covariance matrices will be investigated. The change from baseline in ESSDAI at Week 13 (end of placebo-controlled period) will be estimated from the model. Inference will be done in the frequentist framework.

For Cohorts 1 and 2 the results from the primary analysis will be assessed against the following efficacy criteria:

- a statistically significant reduction in ESSDAI at Week 13 in the CFZ533 i.v. group compared to placebo, at the one-sided 10% significance level, and
- an estimated mean reduction in ESSDAI in the CFZ533 i.v. group to be 5 points or greater than placebo.

The decrease of 5 points was chosen because it is in the range of what was observed at week 12 in a small open-label study with rituximab ([Meiners et al 2012](#)). A positive sign of efficacy will be considered if both criteria are met.

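### As written, patients who stop treatment before Day 85 but stay in the study are not asked for the Week 13 ESSDAI on which the primary estimate rests

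*Protocol*

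**What the plan says.** Protocol 5.5.10 separates stopping treatment from leaving the study: "Subjects who discontinue study treatment should NOT be considered withdrawn from the study UNLESS they withdraw their consent". Its instruction for these patients is: "They should return for the assessments indicated by an asterisk (*) in the assessment table". No other text asks them to keep their scheduled visits.

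In the Cohort 1 assessment schedule the asterisk is attached to V777 (end of study, Week 33, Day 225), with the note "Patients who discontinue the study should complete these assessments". The V777 column includes ESSDAI. Visit 8 (Week 13, Day 85) carries footnote 2, which only marks the change of period.

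The Cohort 2 grid is not in the available text. Protocol 3.1 states: "The study design for Cohort 2 is identical as Cohort 1 with the exception of the dosing regimen". In the footnotes that appear to be Cohort 2's, the discontinuation note is number 3. The one asterisk note after the Cohort 1 table reads "Baseline safety evaluation results must be available prior to dosing and meeting eligibility criteria"; whether it belongs to Cohort 2 or Cohort 3 cannot be told.

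On the analysis, SAP 7.1.1 fits a model to data up to Week 13 with baseline, treatment, visit and treatment-by-visit terms, and states: "The change from baseline in ESSDAI at Week 13 (end of placebo-controlled period) will be estimated from the model". Protocol 9.4.3 and the matching SAP text assume missing at random and say that the discontinuation guidelines "should ensure that the missingness mechanism is as close as possible to missing at random".

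**The concern.** The primary estimate is a Week 13 contrast. Protocol 5.5.10 defines a group who are still consenting and reachable, but who are not asked for the Week 13 value. This includes a patient who has had all four controlled-period doses (Days 1, 15, 29 and 57) and stops before Day 85. The missing-at-random assumption is tied to the discontinuation guidelines, and those guidelines create the gap.

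The model must then supply the Week 13 values of these patients from baseline, their earlier scheduled ESSDAI scores and the other patients in the arm. If those who stop differ at Week 13 in ways their earlier scores do not show, the arm mean is off. Under the SAP's analysis within cohort, Cohort 2 has about 10 randomized placebo patients (30 at 2:1), so each missing placebo value has appreciable weight.

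**Working it through.** **Inputs**
- Cohort 2: about 30 randomized, about 24 completing (Protocol 3.1); allocation 2:1 (3.2).
- Analysed: 16 CFZ533 and 8 placebo, SD 5 (9.6).
- Success: one-sided 10% significance and an estimated advantage of at least 5 points (9.4.2; SAP 7.1.1).

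**Step 1: reproduce the plan's figures.** SE = 5 × √(1/16 + 1/8) = 2.165. Significance needs 1.2816 × 2.165 = 2.77 points, so the 5-point criterion governs and P(both) = 1 − Φ((5 − d)/2.165).

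| True difference d | Plan | Formula | Simulation with t test (200,000 runs) |
|---|---|---|---|
| 7 | about 83% | 82.2% | 82.4% |
| 5 | about 51% | 50.0% | 50.2% |
| 2 | below 10% for less than 2 | 8.3% | 8.3% |
| 0 | about 1% | 1.05% | 1.03% |

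The sample size section is sound on its own inputs.

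**Step 2: share without a Week 13 value.** 1 − 24/30 = 20%, or 6 of 30. This is an upper limit for the affected group, because some of the six will have withdrawn consent.

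**Step 3: size of a possible shift (assumption).** Suppose 20% of one arm only are truly x points worse at Week 13 than the model predicts. That arm's mean is then too favourable by 0.2x: 0.6, 1.0 or 1.4 points for x = 3, 5 or 7. With 10% missing the range is 0.3 to 0.7; with 30%, 0.9 to 2.1. The documents give no value for x.

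**Step 4: effect on the decision (16 vs 8, SE 2.165).**

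| Shift | Placebo only: P(both) at true 7 | CFZ533 only: P(both) at true 0 |
|---|---|---|
| 0 | 82.2% | 1.05% |
| 0.6 | 1 − Φ((5 − 6.4)/2.165) = 74.1% | 1 − Φ((5 − 0.6)/2.165) = 2.1% |
| 1.0 | 67.8% | 3.2% |
| 1.4 | 60.9% | 4.8% |

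If both arms have the same dropout rate and the same deficit, the shifts cancel and the bias in the difference is zero.

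**The case against.** Several counter-arguments stand and limit the point.

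- **Cohort.** The efficacy criteria concern the i.v. group, which is Cohort 2. The asterisk evidence is from Cohort 1.
- **Mechanism.** The 7-point worsening guidance applies after more than 8 weeks. The next scheduled ESSDAI after Day 57 is Day 85, so many such stops may be decided with the Week 13 value in hand. Stopping on a recorded score that is in the model is compatible with missing at random.
- **Who is missing.** The expected non-completers are not broken down by reason. For those who withdraw consent, Protocol 5.5.11 rules out further assessments.
- **Stakes.** The study is non-confirmatory, the criteria support internal decisions, and even 4.8% is below the 10% level. The SAP also says that the missing-at-random assumption will be checked, with further methods if needed, although it names none.

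Two stronger readings are tempting and not supported. A reader might infer that an ESSDAI taken on stopping is lost to the visit-based model. The documents do not say that V777 is done on stopping rather than at Day 225, and derived variables are specified in RAP Module 8, which is not available here and could hold a visit-mapping rule. A reader might also infer that the missing patients are those who did badly, or that the model predicts them only from patients who stayed. No text supports the first, and each patient's own earlier scheduled ESSDAI values enter the model.

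None of this removes the central gap: no text available asks a consenting patient who stops before Day 85 for the Week 13 score.

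**Conclusion.** The gap holds on the plain text for Cohort 1. For Cohort 2 it holds by the statement that the design is identical apart from dosing, with a mismatch in markers that itself needs reconciling. It affects stops before Day 85 without withdrawal of consent, at most about 6 of 30 patients in Cohort 2.

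The bias is of unknown size and direction. The 0.6 to 1.4 point shift assumes 20% missing and a 3 to 7 point deficit, all in one arm. On that assumption the chance of meeting both criteria at a true 7 points falls from 82% to between 74% and 61% if the arm is placebo. If it is CFZ533, the false-positive chance rises from 1.0% to between 2.1% and 4.8%. These are illustrations of sensitivity in a small trial. They do not show that the primary result is biased. The change is worth making because it reduces missing primary data at little cost.

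**What to change.** **Protocol.** Amend 5.5.10 and the schedules so that patients who stop treatment without withdrawing consent are asked for the remaining scheduled ESSDAI assessments through Week 13. Make the asterisk and numbered footnotes mean the same thing in every cohort table, and state whether V777 is done on stopping or at Day 225. No dose or stopping criterion changes.

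**SAP.** Use the off-treatment Week 13 values at least in a stated sensitivity analysis. Whether they also enter the primary analysis is a choice of estimand and should be written down. State how an ESSDAI from a V777 held before Day 85 enters the model: a window by study day, and a rule for when that visit already has a value. A bare nearest-visit rule is too loose, since it would label a Day 72 score as Week 13 (the midpoint of Days 57 and 85 is Day 71). If RAP Module 8 already covers this, a cross-reference is enough. The mapping recovers nothing if V777 is held at Day 225.

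**Cost.** Mainly one extra visit for up to about six patients, and wording in the SAP. The collection change helps only patients who have not yet passed Week 13. Protocol 3.1 sends all new patients to Cohort 3 after Amendment 6, and SAP section 3 notes that interim analyses have already occurred, so for Cohorts 1 and 2 the SAP changes may be the only part still available.

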5.5.11 Withdrawal of consent

Subjects may voluntarily withdraw consent to participate in the study for any reason at any time.

Withdrawal of consent occurs only when a subject does not want to participate in the study anymore and does not want any further visits or assessments and does not want any further study related contacts and does not allow analysis of already obtained biologic material.

If a subject withdraws consent, the investigator must make every effort to determine the primary reason for this decision and record this information. Study treatment must be discontinued and no further assessments conducted. All biological material that has not been analyzed at the time of withdrawal must not be used. Further attempts to contact the subject are not allowed unless safety findings require communicating or follow-up.

5.5.12 Loss to follow-up

For subjects whose status is unclear because they fail to appear for study visits without stating an intention to withdraw, the investigator should show “due diligence” by documenting in the source documents steps taken to contact the subject, e.g., dates of telephone calls, registered letters, etc. A subject should not be considered lost to follow-up until his/her scheduled end of study visit would have occurred.

Subjects dropping out for reasons other than safety without at least one post-baseline ESSDAI result will be replaced by an equal number of newly enrolled subjects.

5.5.13 Emergency breaking of assigned treatment

Cohorts 1 and 2:

Emergency unblinding in Cohorts 1 and 2 should only be undertaken when it is essential to treat the subject safely and efficaciously. Most often, study treatment discontinuation and knowledge of the possible treatment assignments are sufficient to treat a study subject who presents with an emergency condition. A complete set of emergency code break cards will be provided to the investigator site(s) and a complete set will be available at Novartis. All code break cards must be retained until the end of the study and returned to Novartis. They must be stored in a secure place but be accessible in case of emergency. The investigator will receive a blinded code break card for each subject, with the details of drug treatment covered by a removable, scratch-off cover. In an emergency, the scratch-off cover can be removed to determine the treatment. The scratch-off covers are not to be removed for any reason other than an emergency. When the investigator removes the scratch-off cover he/she must note the

date, time, and reason for removing it and retain this information with the case report form documentation. **The unblinded treatment code should not be recorded on the eCRF.** The investigator must also immediately inform the Novartis local monitor that the code has been broken.

It is the investigator's responsibility to ensure that there is a procedure in place to allow access to the code break cards in case of emergency. If appropriate, the investigator will inform the subject how to contact his/her backup in cases of emergency when he/she is unavailable.

An assessment will be done by the appropriate site personnel and the Sponsor after an emergency unblinding to assess whether or not study drug should be discontinued for a given subject and, if applicable, whether the subject can continue into the next trial phase (e.g., an unblinded extension).

Cohort 3 will be open-label.

5.5.14 Study completion and post-study treatment

Each subject will be required to complete the study in its entirety and thereafter no further study treatment will be made available to them. The study will complete when the last subject completes their Study Completion visit, and any repeat assessments associated with this visit have been documented and followed-up appropriately by the Investigator.

After study participation, the patients will continue to be treated by his/her general practitioner according to the local standard clinical management related to the underlying disease.

The investigator must provide follow-up medical care for all subjects who are prematurely withdrawn from the study, or must refer them for appropriate ongoing care.

5.5.15 Early study termination

The study can be terminated at any time for any reason by Novartis. Should this be necessary, the subject should be seen as soon as possible and treated as a prematurely withdrawn subject. The investigator may be informed of additional procedures to be followed in order to ensure that adequate consideration is given to the protection of the subject's interests. The investigator will be responsible for informing IRBs/IECs of the early termination of the trial.

6 Visit assessments

The full [Assessment schedule](#) is presented at the end of the synoptic section, above.

Subjects should be seen for all visits on the designated day with an allowed “visit window” as shown below:

1. Baseline visit assessments (V2, Day -1, Week -1) can be started from Day -6.
2. Visit V3 (Day 1, Week 1) should occur within 7 days after the Baseline visit (V2, Day -1, Week -1)
3. Subsequent visits starting from V4 up to V12 in Cohorts 1 and 2, or from V4 up to V15 in Cohort 3, inclusive: ± 3 day
4. Visits V13, V14 and V777 in Cohorts 1 and 2, or V16, V17, V18 and V777: ± 7 days

Every effort should be made to take the pharmacokinetic samples at the protocol specified time. When assessments are scheduled to be performed at the same time-point, these will be taken after the pharmacokinetic sample and other blood samples.

ECGs must be recorded after 10 minutes rest in the supine position to ensure a stable baseline. The preferred sequence of cardiovascular data collection during study visits is ECG collection first, followed by vital signs.

At a minimum, subjects will be contacted for safety evaluations during the 30 days following the last study visit or following the last administration of study treatment if there are post-treatment follow-up visits (whichever is later), including a final contact at the 30-day point. Documentation of attempts to contact the subject should be recorded in the source documentation.

